# Version History

Version	Date	Author	Changes
DRAFT Versions	13.05.2015	[name] [name]	Initial development
Version 1.0	31.08.2017	[name]	Update, minor changes
Version 1.1	21.12.2018	[name] [name]	definition changes in Analysis sets, adapt to updated FU windows and handling follow-ups, add analysis specifications and details in endpoint relevant calculations, add subgroup analysis and comparisons (appendix), adding EFAS (analysis set)  Updates according to Quality Meeting of 25 th of October 2018

# Abbreviations

12MFU	12 months follow-up
ACE inhibitors	Angiotensin-Converting
ACT	Activated Clotting Time
AE	Adverse Event
AF	Atrial Fibrillation
AFEQT	Atrial Fibrillation Effect on Quality of Life (Questionnaire)
Afl	Atrial Flutter
ASA	AcetylSalicylic Acid
AT II antagonist	Angiotensin Receptor II Antagonist
AV-Block	AtrioVentricular Block
CABG	Coronary Artery Bypass Graft
CFAE	Complex Fractionated Atrial Electrograms
cGy	CentiGray
CHA2DS2-VASc	Score for Stroke Risk Components: cardiac failure, hypertension, age $\geq 75$ (doubled), diabetes, stroke (doubled)-vascular disease, age 65–74 and sex category (female)
CI	Confidence Interval
CIP	Clinical Investigational Plan
cm	Centimeter
COPD	Chronic Obstructive Pulmonary Disease
CRF	Case Report Form
CRO	Contract Research Organisation
CRT	Cardiac Resynchronization Therapy
CT	Computed Tomography
CV	Cardio Version
CVD	Cardiovascular Disease
DAP	Dose Area Product
dd.mm.yyyy	Date with Day.Months.Year
EBogen	Electronic Data Capture System of the Institut für Herzinfarktforschung
ECG	Electrocardiogram
eCRF	Electronic Case Report Form
EDC	Electronic Data Capture
EGM	Electrogram
EHRA	European Heart Rhythm Association
EP	Electrophysiology
FU/GFU	Follow-up/General Follow-up
GmbH	Gesellschaft mit beschränkter Haftung (limited liability company)
HAS-BLED	Score for Major Bleeding Risk Components: hypertension, abnormal renal/liver function (1 point each), stroke, bleeding history or predisposition, labile INR, elderly ( $>65$ ), Drugs/alcohol concomitantly (1 point each)
HF	Heart Failure
hh:mm	Time with Hours.Minutes
ICD	Implantable Cardioverter-Defibrillator
ICM	Implantable Cardio Monitor
IHF	IHF GmbH - Institut für Herzinfarktforschung, Ludwigshafen

ILR	Implantable Loop Recorder
INR	International Normalized Ratio
IPG	Implantable Pulse Generator
IVC	Inferior Vena Cava
kg	Kilogram
LA	Left Atrium
LAAO	Left Atrial Appendage Occluder
LCPV	Left Common Pulmonary Vein
LIPV	Left Inferior Pulmonary Vein
LMWH	Low-Molecular-Weight Heparin
LSPV	Left Superior Pulmonary Vein
LV	Left Ventricle
LVEF	Left Ventricular Ejection Fraction
MAAC	Multi-Array Ablation Catheter
MASC	Multi-Array Septal Catheter
MDT	Medtronic
mGy*cm 	MilliGray Square Centimeters
MI	Myocardial Infarction
min	Minute
ml	Milliliter
mm	Millimeters
mmHg	Millimeters of Mercury
MRI	Magnet Resonance Imaging
NA	Not Applicable
NIS	Non-interventional Study
no.	Number
NOAC	Novel Oral Anticoagulant
NSAID	NonSteroidal Anti-Inflammatory Drugs
NSR	Normal Sinus Rhythm
NYHA	New York Heart Association
Op	Operator
PAF	Paroxysmal Atrial Fibrillation
PCI	Percutaneous Coronary Intervention
PDRF	Patient Data Release Form
PIC	Patient Informed Consent
PV	Pulmonary Vein
PVAC	Pulmonary Vein Ablation Catheter
PVI	Pulmonary Vein Isolation
Q1	Lower Quartile
Q3	Upper Quartile
QoL	Quality of Life
RA	Right Atrium
RF	Radiofrequency
RFA	Radiofrequency Ablation
RIPV	Right Inferior Pulmonary Vein
RMPV	Right Middle Pulmonary Vein
RSPV	Right Superior Pulmonary Vein
SAE	Serious Adverse Event

SAP	Statistical Analysis Plan
SAS	Statistical Analysis System
SD	Standard Deviation
sec	Second
SVC	Superior Vena Cava
TEE	Trans-Esophageal Echocardiography
TIA	Trans-Ischaemic Attack
TTE	Trans-Thoracic Echocardiogram
VF	Ventricular Fibrillation
VKA	Vitamin K Antagonist
VT	Ventricular Tachycardia

# 1 Introduction

## 1.1 General Information

The intention of this Statistical Analysis Plan is to specify procedures regarding all planned statistical analyses within the framework of the GOLD AF registry performed by the IHF GmbH - Institut für Herzinfarktforschung, Ludwigshafen. The overall objective of the SAP is to ensure the credibility of the study data by describing the statistical methodology to be used to evaluate the baseline and follow-up data of the GOLD AF registry.

The initial version of the Statistical Analysis Plan will be completed before first database lock. However, any of the following points may become subject to alterations during the course of the study. Significant changes to statistical analyses shall be discussed with the Statistical Analysis Plan approvers prior to their implementation. All parties affected by changes are to be informed by the author of the changes.

If necessary, selected tasks may be delegated to authorised and adequately qualified designees by the assigned personnel without the need to update the Statistical Analysis Plan. However, the responsibilities remain with the personnel assigned in the Statistical Analysis Plan.

By the time of database lock, the Sponsor Project Responsible shall receive the final version of the Statistical Analysis Plan.

This is a non-interventional registry. The statistical analysis will be performed on an exploratory and descriptive basis and there are no initial hypotheses to be tested.

This Statistical Analysis Plan has been written based on the following documents for this prospective non-interventional registry GOLD AF:

- Clinical Investigational Plan (Version 1.0 dated 06-Feb-2015)
- Clinical Investigational Plan (Version 2.0 dated 09-Sept-2016)
- Case Report Form (Version 1.3 dated 30-APR-2015)
- Case Report Form (Version 1.4 dated 13-Jan-2017)
- Annotated Case Report Form (Version 1.3) – Appendix E
- Annotated Case Report Form (Version 1.4) – Appendix E
- Data Management Plan (V1.2 dated 05-Jul-2016)
- Online Data Validation Plan (V1.0 dated 21-SEP-2015)

## 1.2 Statistical Site

The statistical analysis of this registry will be performed by the following Contract Research Organisation (CRO):

## 1.3 Software

Statistical analysis will be carried out using SAS®, release 9.3 or higher (SAS Institute Inc., Cary, NC, USA) on a Microsoft® Windows® 7 or a Microsoft® Windows® 10 Enterprise platform.

## 2 Objectives of the Non-interventional Study

### 2.1 Main Objective

The primary objective of this study is to assess the Phased RF ablation success rate after 12 month follow-up in patients with AF who are scheduled for Phased RFA.

### 2.2 Secondary Objectives

Ancillary objectives of this study are as follows:

- Estimate Phased RFA safety
- Characterize the acute procedural success rate
- Assess Phased RFA efficiency
- Characterize the peri-procedural anticoagulation therapy
- Describe single catheter PVAC GOLD utilization in persistent AF
- Evaluate QoL ("AFEQT" questionnaire)

## 3 Study Design

### 3.1 Design

The GOLD RF registry is a postmarket release (PMR), prospective, observational, multi-centre, clinical study in consecutive subjects with atrial fibrillation treated with the phased RFA technology (Medtronic, Minneapolis, MN, USA). Patient's participation in this study has no impact on his or her indication, diagnostics or therapy. Subjects are supposed to be treated in compliance with current valid Instructions for Use (IFU) as well as according to medical society guidelines and the clinic's internal directives. Medication-based therapy should also meet medical society guidelines or the clinic's internal directives, respectively.

[figure not shown]
40 sites in 14 countries (Germany, Netherlands, United Kingdom, Hungary, Italy, Spain, Switzerland, Israel, Poland, Portugal, France, Greece, Georgia and South Korea) are anticipated to take part in the registry to get documentation on at least 800-1000 patients (for more details regarding sample size consideration, see Section 3.3 in the SAP). Eligible for participation are study sites and hospital-based physicians treating AF subjects with phased RFA technology. The enrolment period is estimated to be 24 months. The individual observation period per patient is up to 12 (+2) months: Based on the observational plan, it is planned that the baseline visit is conducted by the investigators. All follow-up visits in the registry are unscheduled. They will be conducted in accordance with "routine clinical practice" in the participating medical centres: Between the procedure date and the following 12MFU period, any general FU will be captured. General FUs might occur due to site specific visit schedule, related to AF re-occurrence (re-ablation, AF symptoms, CV etc.) or due to patient visits at the site because of AE related symptoms. At 12MFU window, the patient will either be followed up in the medical centre or by phone.

## 3.2 Flow Chart

Data Collection*	Baseline	Procedure first docu- mented, additional	General Visit/ FU	12 months FU in hospital	12 months FU by phone
Enrolment (PIC/PDRF)	X				
Demographics	X				
Medical History #	X				
Concomitant disease	X				
Diagnostics	X		X	X	X
Symptoms			X	X	X
Medication list	X		X	X	X
Administrative information		X	X	X	X
Anticoagulation pre-intra- procedural		X			
General procedure summary		X			
Consumables		X			
PVI confirmation		X			
Hospital discharge		X			
Quality of Life (AFEQT)	X			X	X
History of AF since last visit			X	X	X
Hospitalization			X	X	X
Adverse events (AEs)	- Whenever occur -				

\* = prior to first patient enrolment every site needs to fill in a site questionnaire once

# = Medical history includes questions about prior CVD, history of AF, main underlying disease, concomitant disease and history of AF.

**Figure 1:** Study design – flow chart.

### 3.3 Sample Size Determination

The sample size calculation is based on the main objective to document real life mid-term efficacy of patients with atrial fibrillation who were scheduled for phased RF ablation. Efficacy is in this case assumed as the proportion of redo ablations 12 months after treatment.

The table below shows the sample size needed for estimating a binomial proportion for given prevalence with corresponding precision.

**Table 1:** Cross table for precision and prevalence for sample size assessment.

Prevalence	Precision			
	1%	2.5%	5%	10%
0.1	4150	665	167	42
0.2	7377	1181	296	75
0.3	9682	1550	388	98

Precision = half-width of a 95% CI

Design effect = 1.2 (variance inflation due to cluster sampling design)

Low sampling rate assumed to have no impact on sample size calculation

Assuming a prevalence of re-ablation 12 months after treatment of 20%, a sample size of 800 will allow the study to estimate the prevalence with a given precision of  $\pm 3.8\%$  [range of 95%-CI: 7.6%]. This size guarantees sufficient information to estimate the prevalence in smaller subgroups (e.g. subgroup with a prevalence of 25% with a precision of  $\pm 6.6\%$  [range of 95%-CI: 13.3%]).

A drop-out rate of 25% is assumed (i.e. an estimated drop-out of about 200 patients). Thus, it is planned to enrol a total number of patients of at least 800 - 1000.

## 4 Analysis Sets

Analysis sets will be predefined and selected for each analysis to be carried out, based on the scope of the analysis. The Appendix B will give an overview about analysis tables, study objectives and analysis sets. Analysis sets might be used for further analysis. The following analysis sets will be applied:

### 4.1 All-Documented Patient Set

The *All-Documented Patient Set* (APS) consists of all patients with signed patient informed consent (PIC) and complete date of PIC who have any additional eCRF documentation, i.e. with non-empty eCRF information for at least one further collection point. In case of a missing PIC/PDRF or an incomplete date of PIC/PDRF, the entry for that patient in the database is only formally created and no further information (at least on further eCRF pages) can be added.

In case that a given PIC/PDRF is drawn back during the course of the registry (i.e. PIC/PDRF is set from "yes" to "no" during the visit), entries that have already been made are not deleted. These entries should be set to missing in the analysis data sets.

If a patient exits from the study, data collected prior to the study withdrawal will be included in the analysis in compliance with PIC/PDRF unless the patient object and ask for deletion of the data or when required by local regulations.

The APS will be used for total registry analysis (interim, final and post-hoc analysis).

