4.1 Registry Population

Data from all patients who are enrolled in the study (patients who meet the eligibility criteria and have signed the PIC/PDRF) will be included in the analysis. If a patient exits from the study, data collected prior to the study withdrawal will be included in the analysis.

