The "Procedure" CRF will be used to collect data about the ablation procedure and discharge from the medical center. Information regarding anticoagulation therapy, procedure summary information, sedation and consumables, PVI confirmation, cardiovascular medication, date and status at hospital discharge is to be collected. Verification of study defined AEs will be done during the procedure and at the moment of hospital discharge.

If the attempt to conduct Phased RFA ("index" procedure) is not successful for clinical or technical reason, patients will stay enrolled into the registry. If Phased RFA is repeated ("repeated" procedure) or re-do due

to arrhythmia recurrence, the “procedure” CRF should be filled in. Information about all Phased RFA attempts will be used for the analysis. If patient has re-do procedures with some other technology than Phased RFA, Procedure CRF is not required; information about technology which was used for re-ablation to be collected in eCRF “General FU”.

During the Phased RFA, the investigator may require use of other commercially available devices for other ablations such as Afi/LAT or other AF triggers. The use of other devices will be at the investigator’s discretion and use will be documented on the eCRF.

Hospital discharge needs to be completed when the patient is discharged from the hospital, this data to be collected as a part of the procedure visit. Information about date of discharge, reportable adverse event since the procedure and recommended medication information is to be collected. Post-ablation drug regimen is determined at clinical discretion of the treating investigator.

General Follow up visits (in hospital)

The “General” FU CRF will be used to collect data during all standard visits at the site within the following 12 months after the index or study procedure. Data to be collected include: arrhythmia assessment, diagnostics, symptoms, hospitalizations, ablation information and medication. If “General FU” will take place due to system/procedure related AE, “Adverse Event” CRF should be filled in additionally to the “General” FU CRF.

If at any moment during FU, the patient withdraws PIC/PDRF or PI receives information about the patient’s death, the “Exit” CRF should be filled in addition to the “General FU” CRF. All data collected prior to the patient exit will be used for analysis, unless different is required by local laws and regulations.

12 months FU (in hospital or by phone)

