# 6 Target Variables

## 6.1 Study Population

Data from all patients who are enrolled in the study (patients who meet the eligibility criteria and signed the PIC/PDRF) will be included in the analysis. If a patient exits from the study, data collected prior to the study withdrawal can be included in the analysis in compliance with PIC/PDRF unless patient requests deletion of the personal data when exit the study in compliance with local regulations.

The following parameters will be used to characterise the study population and to give an overview on the documented visits:

- Overview about patient status
  - number of patients in the All-Documented Patients Set (APS),
  - number of patients in Baseline Analysis Set (BAS),
  - number of patients in Full Analysis Set (FAS)
  - number of patients in Extended Full Analysis Set (EFAS)
- Overview about reasons for being excluded from the different analysis sets
  - Criteria for the BAS
  - Criteria for the FAS
- Number of documented patients per site (BAS)
- Number of documented patients per visit and visit period (FAS)
- Number of documented visits per patient (FAS)
- Number of documented patients by visit pattern (FAS)

A patient is defined as "documented" at a respective visit, if the FU form has a date of the visit and it is non-empty (at least one further entry) for that visit.

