## 7 Data Handling

This chapter contains instructions for data handling which are generally decisive for derived variable calculations and data presentation.

The basis for time calculations will be the first documented procedure (SAP chapter 7.4.1).

In order to assess the effects of patients lost to follow-up, percentages of dropouts and reason for loss to follow-up will be summarized. In addition, baseline characteristics of patients who were lost to follow-up in comparison to patients with a complete follow-up will be described (SAP chapter 8.6). Patients who withdrawal the PIC/PDRF will be handled according to SAP chapter 6.1.

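### SAP 4.1 sets the earlier entries of patients who withdraw consent to missing, against Protocol 4.1 and 7.2, SAP 6.1 and 7, and its own next paragraph; complications could drop out of the BAS safety analysis

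*SAP*

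**What the plan says.** SAP 4.1 (All-Documented Patient Set), second paragraph, opens with the trigger: "In case that a given PIC/PDRF is drawn back during the course of the registry". It identifies this by the eCRF consent field changing from yes to no. In the database, "entries that have already been made are not deleted". In the analysis, "These entries should be set to missing in the analysis data sets". No condition or exception is attached.

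The other places that deal with the point say something else:

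- **Protocol 4.1 (Registry Population):** for a patient who exits, "data collected prior to the study withdrawal will be included in the analysis".
- **Protocol 7.2 (General Follow up visits):** this paragraph names withdrawal of the PIC/PDRF during follow-up, asks for an Exit form, and continues: "All data collected prior to the patient exit will be used for analysis, unless different is required by local laws and regulations".
- **Protocol 7.2 (Study Exit):** consent withdrawal is given as an example of exit by patient choice.
- **SAP 4.1, third paragraph:** for a patient who exits, "data collected prior to the study withdrawal will be included in the analysis in compliance with PIC/PDRF unless the patient object and ask for deletion". Local regulations are a further exception.
- **SAP 7 (Data Handling):** "Patients who withdrawal the PIC/PDRF will be handled according to SAP chapter 6.1".
- **SAP 6.1 (Study Population):** "data collected prior to the study withdrawal can be included in the analysis in compliance with PIC/PDRF", unless the patient requests deletion.

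**The concern.** A patient who has been ablated, has a complication and then withdraws consent is treated in opposite ways depending on which sentence the programmer follows. Under the second paragraph of SAP 4.1 the procedure and the event are blanked. Under the remaining text they are kept, subject to the stated exceptions.

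Patients who withdraw after a complication need not resemble those who stay. If their risk is higher, blanking them lowers the reported complication rate. Serious events in this registry are expected to be few, so losing a handful of cases is noticeable. The drop-out summary promised in Protocol 4.2 and SAP 7 could also be affected, because withdrawers are among the patients it should describe.

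**Working it through.** **1. Do the rules cover the same patients?** One might try to separate a consent form drawn back (SAP 4.1, second paragraph) from a study exit (third paragraph). That does not work. Protocol 7.2 and SAP 7 both name PIC/PDRF withdrawal, and Protocol 7.2 lists consent withdrawal under study exit. The blanking sentence has no condition. The keep rules do: the signed PIC/PDRF, a deletion request, or local law.

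**2. Is it a declared departure from the protocol?** Protocol 4.4 asks for changes to its analysis methods to be described and justified in the SAP. The SAP says so openly when it drops the protocol's visit windows (SAP 7.2.3) and its recurrence definition (SAP 8.1.1). It makes no such statement about withdrawals.

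**3. Which analyses are exposed?**

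- The APS needs non-empty eCRF information beyond consent. The BAS (SAP 4.2) needs APS membership, a procedure date, the PVAC GOLD catheter and more than zero PV applications. With these fields blanked, the patient meets neither definition and leaves both numerator and denominator.
- Safety (SAP 8.2.1) is calculated for the BAS and the FAS. The BAS definition needs no 12-month form, so BAS safety is the main exposure.
- The FAS (SAP 4.3) needs a valid signed 12-month form, and the EFAS (SAP 4.4) is a subset of it. A patient who withdraws before that form is outside both sets under either rule. Completing the form ends participation.
- Recurrence is to be calculated for the BAS, FAS and EFAS, but SAP 8.1.1 also says that the BAS and FAS patients concerned need a signed 12-month form. Whether early withdrawers would have counted at all is therefore unclear.
- Lost-to-follow-up tables use the APS and BAS (SAP Appendices C and D). SAP 4.1 blanks entries already made and does not say whether a later Exit form is included, so this effect is possible but not established.

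**4. Possible size for safety.** The plan has no figure to reproduce. Inputs:

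- Complication rate 3.9% in all patients: the European survey figure in Protocol 4.4.2, used as an illustration.
- Enrolment 1000: Protocol 4.3.
- Share withdrawing, w: not in the documents; assumed 1% to 5%.
- Risk in withdrawers, r: not in the documents; assumed from 3.9% (equal risk) to 10%.

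Reported rate after blanking = (0.039 − w × r) / (1 − w).

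- r = 3.9%: 0.039 × (1 − w) / (1 − w) = 3.9% for any w, so there is no bias.
- r = 10%, w = 1%: (0.039 − 0.001) / 0.99 = 3.84%.
- r = 10%, w = 3%: (0.039 − 0.003) / 0.97 = 3.71%.
- r = 10%, w = 5%: (0.039 − 0.005) / 0.95 = 3.58%.

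In the last case 50 of 1000 patients are removed, taking 50 × 0.10 = 5 of 39 complications with them.

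A harsher assumption takes 3.9% as the risk in those who stay and four times that, 15.6%, in withdrawers. At w = 5%, 50 × 0.156 = 7.8 complications are lost, and 3.9% is reported where the full rate is 0.95 × 3.9% + 0.05 × 15.6% = 4.485%.

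For scale, the 95% half-width at 3.9% and n = 1000, ignoring clustering, is 1.96 × √(0.039 × 0.961 / 1000) = 1.2 percentage points.

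**The case against.** The strongest reply is that the SAP already holds the right rule. SAP 7 is the data-handling chapter and sends PIC/PDRF withdrawals to 6.1, and the third paragraph of SAP 4.1 keeps the data. The blanking sentence follows text on missing consent entries and is tied to a switch of the eCRF consent field. The protocol documents withdrawal on an Exit form and does not mention that switch, so few ordinary withdrawers might be touched. This stands as a limit on how certain the loss is. It does not remove the conflict: the sentence speaks of the course of the registry, and nothing in the SAP says that 6.1 overrides it.

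A reader might infer that withdrawers' complications and recurrences disappear from every analysis set, and that the success rate is thereby raised. The documents do not support that. The keep rules make the loss possible rather than certain. Early withdrawers are outside the FAS and EFAS in any case, and the signed-form requirement in SAP 8.1.1 leaves the recurrence effect open.

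Two further objections hold. The 10% risk has no source, and even at 5% withdrawal the shift (3.90 − 3.58 = 0.32 points) is well inside the 1.2-point half-width. And retention cannot be unconditional: SAP 4.1 and 6.1 tie it to compliance with the PIC/PDRF, and 6.1 says only that the data can be included. The protocol and SAP text does not show what the signed forms provide on withdrawal.

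**Conclusion.** The contradiction is established from the text alone: one unconditional sentence in SAP 4.1 conflicts with Protocol 4.1 and 7.2, with SAP 7 and 6.1, and with the paragraph that follows it. Two programmers working from this SAP could build different BAS data sets and report different complication rates.

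The effect is conditional on the sentence being programmed as written. It then falls mainly on BAS safety and possibly on the drop-out description. FAS and EFAS results are largely unaffected, and no conclusion about the success rate is warranted. On the assumptions shown, the complication rate would move from 3.9% to between 3.84% and 3.58%, and not at all if withdrawal is unrelated to complications. Neither the withdrawal share nor the risk in withdrawers can be taken from the documents. The expected bias is small, but it is avoidable and should be removed before the final analysis.

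**What to change.** Replace the set-to-missing sentence in SAP 4.1 with the rule of Protocol 7.2 and SAP 6.1:

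- Data collected up to withdrawal stay in the APS and BAS, in compliance with the signed PIC/PDRF, and time-to-event analyses censor at last study contact, as SAP 8.1.2 already provides.
- Entries are set to missing only if the patient asks for deletion, or if the PIC/PDRF or local regulations require it.
- The report states how many patients were removed for that reason.

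The cost is one SAP edit and one data set derivation. No new data are needed, and the change restores the protocol's own rule.
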